## **12.5 Study Discontinuation**

If the study is discontinued, enrolled subjects will continue to be followed for safety assessments as specified in the protocol.

## 14 SUPPLEMENTS/APPENDICES

### 14.1 Appendix A: Study Schedule

Visit #	1	2	3	4 &	5 &	Final*		
Procedures	D1	D2 +1	D8 +2	D9 +2	D15 +3	D27 - D38	Unscheduled Visit (If needed)	Premature Discontinuation
Signed Consent Form	X							
Inclusion/Exclusion Review	X							
Complete Medical History	X							
Concomitant Medications	X	X	X	X &	X &	X	X	X
Interim Medical History		X	X	X &	X &	X	X	X
Sign Optional Consent For Microneedle Patch 2/3	(X )		(X)					
Application of microneedle patch	X		X &					
Distribute memory aid, ruler & thermometer	X		X &					
Review memory aid		X	X	X &	X &	(X)	(X)	(X)
Physical Exam	Complete Physical Exam	X						
	Assessment of microneedle patch application site	X* *	X	X* *&	X &	X &	X	X
	Symptom-Directed Physical Exam		(X)	(X)	(X) &	(X) &	(X)	(X)
	Height and weight	X						
	Vital Signs ^	X	X	X	(X) &	(X) &	X	X
Photograph site of placebo microneedle patch	(X )	(X)	(X)	(X)	(X)	(X)	(X)	(X)
Assessment of Adverse Events and SAEs	X* *	X	X	(X) &	(X) &	X	X	X
Acceptability Questionnaire	X	X	X	(X) &	(X) &	X	X	X

\* The final study visit will be a telephone call at D27 – D38

\*\* Occurring 15 minutes and 30 minutes after microneedle patch removal.

& At Day 8 the LARs of subjects who no ongoing solicited or unsolicited general AE or local AEs will have the opportunity to decide to have second and third placebo microneedle patches placed at different body sites from the initial location. In those that elect to have a second/third placebo microneedle patch placed, they will return for clinic visits on Day 9 and Day 15.

^ Vital signs will include temperature and pulse.

(X) – As indicated/appropriate.

## 14.2 Appendix B: Adverse Event & Reactogenicity Grading - LOCAL SITE REACTIONS

	LOCAL SITE REACTIONS			
	Grade			
	0	1	2	3
Induration/ Swelling *	None to less than 2.5 cm	2.5 – 5 cm and does not interfere with activity	5.1 – 10 cm or interferes with activity	> 10 cm or prevents daily activity, erosion, or ulceration
Erythema**	None to less than 2.5 cm	2.5 – 5 cm	5.1 – 10 cm	> 10 cm, erythroderma, or a diffuse rash >15% of the body surface area
Ecchymosis	None	2.5 – 5 cm	5.1 – 10 cm	> 10 cm
Tenderness	None	Mild discomfort to touch	Discomfort with movement	Significant discomfort at rest
Pain	None	Does not interfere with activity	Repeated use of non-narcotic pain reliever > 24 hours or interferes with activity	Any use of narcotic pain reliever or prevents daily activity
Pruritus (Itching)	None	Mild	Moderate itching; limiting instrumental activities of daily living	Severe itching; limiting self-care activities of daily living

\*Induration/swelling should be evaluated and graded using the functional scale as well as the actual measurement

\*\*In addition to grading the measured local reaction at the greatest single diameter, the measurement should be recorded as a continuous variable.

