##### Reactogenicity:

- Occurrence of solicited application site reactogenicity (e.g., erythema, induration, bruising, itching) for the 8 days following application of the patch.

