## 9 SAFETY ASSESSMENT AND REPORTING

### 9.1 Definitions

#### 9.1.1 Definition of an Adverse Event (AE)

An AE is any untoward or unfavorable medical occurrence in a human subject, including any abnormal sign (e.g., abnormal physical exam or laboratory finding), symptom, or disease temporally associated with the use of study treatment, whether or not considered related to the study treatment.

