## **9.2 Methods and Timing for Assessing, Recording, and Analyzing Safety Parameters**

All safety parameters will be graded using the scales listed in the Appendices B and C.

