### **9.2.1 Adverse Events**

All AEs occurring while on study during the AE reporting period must be documented appropriately regardless of seriousness, severity, or causal relationship to study product administration. AEs will be recorded on the AE page of the CRF.

Solicited AEs will be collected from Day 1 (after placebo microneedle placement) through Day 8 following placebo microneedle administration (Day 15 in those receiving placebo microneedle patches 2/3). Unsolicited AEs and SAEs will be collected from Day 1 (after placebo microneedle placement) through the Day 27 – 38 end of study visit. AE details will be collected via interview with the subject LAR. Information to be collected includes event description, date of onset, severity and date of resolution/stabilization of the event. Severity and relationship to study product (either “related” or “unrelated”) must be assessed by the Investigator or sub-investigator. Signs and symptoms due to a single diagnosis will be reported as the diagnosis. For example, cough, pharyngitis, rhinitis would be reported as “upper respiratory infection”. If multiple signs/symptoms presenting simultaneously cannot be attributed to the same etiology, then each symptom should be reported separately.

Any medical condition present at the time the subject is screened, or occurring prior to placebo microneedle placement will not be considered an AE, but will be captured in the medical history form. If a preexisting condition worsens (changes in severity or quality, not consistent with the subject’s reported past history of the condition) at any time during the study, this change should be captured as an AE.

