### **9.2.2 Reactogenicity**

Reactogenicity events are reactions that are common and known to or expected to occur following the administration of the study product. Subjects LAR will be provided with a memory aid, thermometer and ruler and will be instructed to record the presence of solicited symptoms and oral temperature through Day 8 after placebo microneedle

placement (Day 15 in those receiving placebo microneedle patches 2/3). If a symptom is still present at Day 8 (Day 15 in those receiving placebo microneedle patches 2/3), the subject LAR will continue to follow that symptom until two days symptom-free. Memory aids will be reviewed and collected by study staff at follow up visits. Reactogenicity event details will be collected via review of the subject's memory aid and by interview with the subject LAR. Memory aid will not be considered source. The subject memory aid will be reviewed with the subject LAR at subsequent visits. Reactogenicity will be analyzed using Appendices B + C.

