##### Reactogenicity:

- Occurrence of solicited application site reactogenicity (e.g., erythema, induration, bruising, itching) for the 8 days following application of the patch.

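### Appendix B pools small erythema and induration with absence and leaves small bruises ungraded, and Section 11.3 does not say what counts as occurrence for the primary reactogenicity endpoint

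*Combined protocol and SAP*

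**What the plan says.** Sections 3.2.1 and 11.1 give the primary reactogenicity endpoint as "Occurrence of solicited application site reactogenicity (e.g., erythema, induration, bruising, itching) for the 8 days following application of the patch". Neither sets a size or grade threshold.

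Two sentences tie this endpoint to the appendix scales. Section 9.2 states: "All safety parameters will be graded using the scales listed in the Appendices B and C". Section 9.2.2 states: "Reactogenicity will be analyzed using Appendices B + C". Under Section 9.2.1, severity "must be assessed by the Investigator or sub-investigator".

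In Appendix B (Section 14.2), Grade 0 for both erythema and induration/swelling is "None to less than 2.5 cm". Induration that interferes with activity is Grade 2 whatever its size. For ecchymosis, Grade 0 is absence only and Grade 1 begins at 2.5 cm. A footnote asks for the measurement as a continuous variable, but its marker is on the erythema row only.

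Section 8.1.5 gives the legally authorized representative (LAR) a different scale. There Grade 0 means the symptom is absent, and Grade 1 is any symptom that is present and well tolerated.

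Section 11.3 plans counts and percentages of subjects and a summary by severity. It does not define when a local sign has occurred, and it plans no summary of diameter.

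**The concern.** The endpoint asks whether a reaction happened, but the scale named for analysing it cannot always answer that. For erythema and for induration that does not interfere with activity, Grade 0 mixes children with no mark and children with a visible or palpable mark under 2.5 cm. For bruising, a small mark cannot be placed on the scale.

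This matters because Section 2.3.1 leads one to expect small reactions: faint, tightly confined, often pinpoint redness that fades over hours or days. How often the patch marks infant skin is a primary question here, and Section 2.3.2 says the results will inform a planned infant vaccine trial. The study is descriptive, so the reported incidence is itself the result.

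There is also a smaller operational effect. Section 9.4 withholds patches 2/3 from a child with an ongoing local reaction of Grade 1 or higher on Appendix B. That rule cannot be applied to a bruise that has no grade.

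**Working it through.** The plan gives no expected reactogenicity rate to reproduce. The probabilities in Section 11.2 concern a generic adverse event rate and do not enter this point.

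**Step 1: where a small reaction falls.** Take a 1 cm reaction that is easily tolerated and does not interfere with activity.

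| Sign | Appendix B Grade 0 | Appendix B Grade 1 | 1 cm on Appendix B | 1 cm on LAR scale (8.1.5) |
|---|---|---|---|---|
| Erythema | absent or below 2.5 cm | 2.5–5 cm | Grade 0 | Grade 1 |
| Induration | absent or below 2.5 cm | 2.5–5 cm, no interference | Grade 0 | Grade 1 |
| Ecchymosis | absent | 2.5–5 cm | no grade | Grade 1 |

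The two scales disagree on whether the same mark is Grade 0 or Grade 1. Section 11.3 names neither as the basis for occurrence.

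**Step 2: size of the possible understatement for erythema or induration.** Let p be the true share of children with the sign at any diameter, and f the share of those whose reaction stays in Grade 0. Both are assumptions; the documents give neither.

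- Rate at Grade 1 or higher = p × (1 − f)
- Understatement, if only Grade 1 or higher is counted = p × f

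| p | f = 0 | f = 1/3 | f = 2/3 | f = 1 |
|---|---|---|---|---|
| 20%: rate at Grade 1 or higher | 20.0% | 13.3% | 6.7% | 0% |
| 20%: understatement (points) | 0 | 6.7 | 13.3 | 20 |
| 60%: rate at Grade 1 or higher | 60% | 40% | 20% | 0% |
| 60%: understatement (points) | 0 | 20 | 40 | 60 |

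**Step 3: the same in counts.** Take a cohort of 25 with 15 children affected at any diameter. Exact (Clopper-Pearson) 95% limits are:

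- f = 0: 15/25 = 60% (38.7–78.9%)
- f = 1/3: 10/25 = 40% (21.1–61.3%)
- f = 2/3: 5/25 = 20% (6.8–40.7%)
- f = 1: 0/25 = 0% (0–13.7%)

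Each child reclassified moves the rate by 1/25 = 4 points.

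**Step 4: what a zero would mean.** The chance that none of 25 reaches Grade 1 is (1 − p(1 − f))^25.

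- p = 20%, f = 2/3: (1 − 0.0667)^25 = 0.178
- p = 60%, f = 0.9: (1 − 0.06)^25 = 0.213

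Taken alone, 0/25 at Grade 1 or higher for one of these signs is compatible with anywhere from 0 to 25 children having had a visible reaction under 2.5 cm.

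**Step 5: bruising.** Let k children have a bruise of 2.5 cm or more and m have only smaller ones. With no grade for the smaller ones, the count at Grade 1 or higher can be anything from k to k + m, depending on who codes it. Coding down loses occurrences. Coding up keeps them but inflates Grade 1 relative to its 2.5 cm cut-point. The direction is not fixed.

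**The case against.** The strongest reply is that the harm needs a table the plan does not specify. The endpoint is occurrence, and no section says that only Grade 1 or higher will be counted. A reader might infer that Grade 0 means no event. The documents do not say so, and the adverse event definition in Section 9.1.1 covers "any untoward or unfavorable medical occurrence in a human subject, including any abnormal sign". This stands: Section 9.2.2 makes a grade-based table a natural reading, not a required one.

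Second, presence is elicited anyway. The LAR is asked to record whether symptoms are present on a scale where any mild reaction is Grade 1. A reader might infer from "Memory aid will not be considered source" that this information is set aside. That goes too far, since the same section collects event details by reviewing the memory aid and interviewing the LAR. What remains is two definitions of Grade 0 and no statement of which one governs.

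Third, erythema is the sign Section 2.3.1 predicts, and its diameter is recorded as a continuous variable, so any-diameter erythema is recoverable at analysis. Induration is also to be graded by actual measurement, although the plan does not ask for the value itself to be kept. The case report forms are not in the documents, so whether fields are missing is not known. For erythema this is a reporting choice, not lost data.

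Fourth, the synopsis, Section 7.3 and Appendix A require no ongoing local adverse event before patches 2/3, without a grade, while Section 9.4 uses Grade 1 or higher. A reader might infer a contradiction, but the texts agree if Grade 0 is not an adverse event. That point is mostly clerical. Only the ungraded small bruise leaves Section 9.4 unusable.

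**Conclusion.** The point holds as a defect in a stated rule. Appendix B has no grade for a bruise above 0 and below 2.5 cm. It merges small erythema and small non-interfering induration with absence, and it disagrees with the scale in Section 8.1.5. Section 11.3 does not say which scale defines the primary occurrence endpoint. Tabulating by Appendix B grade can understate erythema and induration; bruising can be miscoded either way.

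The size is unknown and possibly nil. All values of p and f above are assumptions, and f = 0 gives no effect. A reader might infer from the expected pinpoint erythema that most reactions will be under 2.5 cm. The documents do not establish this: patch size is not given, and the only dimension stated, a 300 µm needle base, does not fix the reaction diameter.

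No hypothesis test or success criterion depends on the point. Itching, pain, tenderness, induration that interferes with activity, the Grade 3 safety endpoint and the study halting rules are untouched. What is at stake is how the incidence of three signs is reported.

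**What to change.** 1. In Section 11.3, define occurrence of erythema, induration and ecchymosis as any visible or palpable reaction (above 0 cm). Report that rate beside the Grade 1 or higher rate, and separate children with no reaction from those with a reaction under 2.5 cm.
2. Together with item 1, assign bruises above 0 and below 2.5 cm a stated grade in Appendix B, so that Section 9.4 can be applied to them. Grade 0 would leave the child eligible for patches 2/3; Grade 1 would not while the bruise is ongoing. Moving small bruises into Grade 0 without item 1 would only extend the pooling to a third sign.
3. Extend the continuous-diameter footnote to induration and ecchymosis.

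The cost is a few table rows and possibly two case report form fields. Rulers are already issued, and erythema diameter is already recorded. Reported rates may look higher, and showing both rates side by side lets the reader see why.

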### 14.3 Appendix C: Adverse Event & Reactogenicity Grading - GENERAL ADVERSE REACTIONS

	GENERAL ADVERSE REACTIONS			
	Grade			
	0	1	2	3
Irritability (fussiness)	None	No interference with activity	Some interference with activity	Significant; prevents daily activity
Lethargy (drowsiness)	None	No interference with activity	Some interference with activity	Significant; prevents daily activity
Decreased appetite	None	No interference with activity	Some interference with activity	Significant; prevents daily activity
Vomiting	None	No interference with activity	Some interference with activity	Prevents daily activity, requires outpatient IV hydration
Fever	None	100.4 – 101.1 F	101.2 – 102.1 F	>102.1 F
